Overall, patients with solid tumors, especially those recently treated with surgery or chemotherapy, appear to be at higher risk than the general population of developing severe or even fatal forms of the viral infection. However, very little data are available regarding:

- the humoral immune response to Covid-19 in cancer patients,
- the risk of respiratory complications,
- comparisons with the general population,
- differences according to systemic treatments received.

In addition, Covid-19 infections are suspected to be more severe in cancer patients due to immunosuppression, but this immunosuppression is highly heterogeneous and poorly assessed in treated or monitored cancer patients.

To date, within the network of French Comprehensive Cancer Centers (CLCC), no study has examined the extent and consequences of the Covid-19 epidemic on service reorganization. Yet this represents an important learning opportunity that could facilitate adaptation during future crises, ensuring optimal management of cancer patients.

Purpose of the study

The aim of this study is to describe the impact of Covid-19 in:

- patients undergoing treatment,
- patients who completed treatment more than one year ago,
- healthcare personnel working in CLCCs,

within a longitudinal study covering several interrelated domains ("Work Packages", WP):

- serological evolution and immune response
- clinical presentation
- epidemiology
- health economics
- psychology

Expected outcomes

We aim to:

- study the evolution of immune response in cancer patients during treatment, compare it with long-term survivors and healthcare workers
- document clinical presentations and determine whether disease course and risk factors depend on specific conditions (e.g., treatment type)
- quantify economic and organizational impacts on care, healthcare personnel, and mobilized health resources
- examine infection modes (epidemiology), despite the challenge created by interactions between the three study populations
- observe the psychological impact of this "period" on healthcare personnel by measuring their anxiety and stress levels

D) GENERAL INFORMATION ABOUT THE TRIAL

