POPULATION:	Population consisting of patients and healthcare personnel from the CLCCs who fall into one of the following 3 categories during the pandemic (between March 2020 and the end of the pandemic): 
 • Patients undergoing treatment, • Patients in follow-up (having completed their treatment more than one year before inclusion), • Healthcare personnel (clinical, medical-technical, and administrative staff) of the institutions.
--------------------	--

METHODOLOGY:	
This is a prospective, multicenter cohort study with the creation of a clinico-biological database, falling within the framework of a category 2 interventional research study (RIPH 2).
 
This research will include:
 
 • The recruitment of patients receiving care in participating centers who attend within the context of their treatment or follow-up during the inclusion period, and the recruitment of healthcare personnel working within these same institutions. • A collection of blood samples (biobank). • Biological and clinical data collected from patient medical records. • Psychometric questionnaires (STAI state, STAI trait, PTGI, HADS) (ANNEXES 8 to 11) and the “Healthcare Personnel” questionnaire (ANNEXE 7) completed by staff. • Sociodemographic, lifestyle, and Covid-19 clinical-symptom questionnaires completed by both personnel and patients (ANNEXES 4 to 6). • PMSI data. • Focus groups with healthcare personnel to explore different behaviors in response to changes. 
A semiannual extraction of data may be considered for exploratory analyses.

NUMBER OF SUBJECTS:	
As this is a cohort study involving the creation of a clinico-biological database, the number of subjects directly depends on the recruitment potential of each center. Based on the information provided by the 4 participating CLCCs, the cohort size has been estimated at 15,000 subjects distributed as follows:
 
 • Number of patients (in treatment and follow-up): 12,000 • Number of healthcare personnel: 3,000
MAIN OBJECTIVE:	
Creation of a clinico-biological database to describe Covid-19 infections (incidence and severity) among CLCC patients and personnel.

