	
Evaluate the neutralizing capacity of IgG (neutralization assays) after vaccination over the duration of the study.
 
WP 2: CLINICAL MANDATORY
 
Describe severity (asymptomatic, symptomatic, prolonged, severe, fatal) by age group:
 
 In healthcare personnel In cancer patients In patients in follow-up In patients undergoing treatment: 
 Receiving chemotherapy and according to whether the chemotherapy induces grade 3–4 neutropenia or lymphopenia (as defined in the primary literature) Receiving immunotherapy 
Determine the frequency of Covid-19 reinfection (recurrence of clinically suggestive symptoms with positive viral PCR and/or positive IgM serology) during follow-up in the different groups.
 
Identify risk factors (clinical and therapeutic) for developing severe forms of Covid-19 infection among patients.
 
WP 3: ECONOMIC ANALYSIS OPTIONAL FOR CENTERS
 
Describe the consequences of Covid-19 in terms of organizational changes and care practices, from the start of the epidemic until the end of systematic screening for patients and healthcare personnel.
 
Identify changes in healthcare personnel practices regarding:
 
Coordination between healthcare workers
 
 Communication Patient management 
Identify resources associated with organizational changes at the level of:
 
 Modification of treatment regimens for patients (e.g., chemotherapy, radiotherapy, surgery) Organization of teleconsultations Diagnostic investigations for new cancers 
Analyze the impact of changes on patient health status.
 
Evaluate resources allocated to:
 
 The organizational changes described above Systematic screening of patients and healthcare personnel Work stoppages. 
WP 4: PUBLIC HEALTH / EPIDEMIOLOGY OPTIONAL FOR CENTERS
 
Identify risk factors for SARS-CoV-2 infection among patients, including:
 
 Sociodemographic factors (age, socio-professional category, housing, cohabitation) Lifestyle (work modalities, mobility, protective measures, etc.) Contact with infected individuals at work or at home Care pathway in CLCCs (number and duration of visits, number of care units visited, etc.), use of community care 
Estimate SARS-CoV-2 infection prevalence at the end of the lockdown:
 
 among patients among healthcare personnel who continued onsite work among healthcare personnel who were confined 
Identify risk factors for Covid-19 infection among healthcare personnel, including:
 
 Sociodemographic factors (age, socio-professional category, housing, cohabitation) Lifestyle (work modalities, mobility, protective measures, etc.)

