	
Time to appearance and titers of anti-SARS-CoV-2 antibodies according to FCGR2A and FCGR3A genotypes.
 
IgG-positive results on rapid TROD tests and semi-quantitative ELISA IgG titers in vaccinated individuals.
 
Number of vaccinated individuals in whom anti-Spike protein IgG titration is feasible.
 
Number of vaccinated individuals with positive neutralization test results.
 
WP 2: CLINICAL MANDATORY
 
Number of Covid-19-related deaths, severe infections (requiring oxygen therapy), prolonged symptomatic infections, moderate infections, and asymptomatic infections, relative to all subjects in the population with seropositivity and/or a positive RT-PCR test, as well as duration of the symptomatic phase.
 
Reinfection cases are defined as recurrence of clinical symptoms and/or positive viral PCR and/or positive IgM serology after a symptom-free interval. Frequency is defined as the number of reinfection cases relative to all subjects in the population with seropositivity and/or a positive RT-PCR test.
 
Among subjects in the population with seropositivity and/or a positive RT-PCR test, factors significantly associated with severe forms / mortality among the following:
 
 ○ Ongoing or recent anticancer treatment: 
 - Immunotherapy - Chemotherapy, according to frequency of grade 3/4 neutropenia and/or lymphopenia - Radiotherapy - Surgery ○ Concomitant treatments ○ Comorbidities ○ Cancer (cancer type, stage, etc.) ○ Cancer-related medical history (number of treatment lines, surgical and medical history) ○ Biological markers (CRP, etc.) 
WP 3: ECONOMIC ANALYSIS OPTIONAL FOR CENTERS
 
Type of organizational and practice changes implemented and their frequency according to specialties/services.
 
Total number of patients affected and number of patients per type of change.
 
Positive or negative effects on patient morbidity or mortality.
 
Monetary value of resources mobilized (increased or decreased) depending on observed changes.
 
Number and duration of healthcare personnel sick leave.
 
Benefits of organizational changes for healthcare personnel.
 
Costs of systematic screening of patients and healthcare personnel..
 
WP 4 : PUBLIC HEALTH / EPIDEMIOLOGY OPTIONAL FOR CENTERS
 
Number of SARS-CoV-2 infections among all monitored patients.
 
Prevalence of SARS-CoV-2 infection/immunization during the 3 weeks following the end of lockdown among patients, healthcare personnel working onsite, and healthcare personnel who were confined, by age group, by region (center), and according to comorbidities.
 
Number of SARS-CoV-2 infections among all monitored healthcare personnel.
 
Quarterly incidence rates among patients and healthcare personnel by age group, by region (center), and according to comorbidities.
 
Percentages (qualitative variables) / means or medians (quantitative variables).

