--	--

	
Percentage of personnel and patients refusing vaccination, and distribution according to reasons for refusal.
 
WP 5 : PSYCHOLOGY OPTIONAL FOR CENTERS
 
a. and b. State anxiety score at 3, 6, 9, and 12 months. c. and d. Depression score at 3, 6, 9, and 12 months.
 
Variables assessed at T0 (before screening) State anxiety (STAI-State questionnaire, Spielberger, Gorsuch, Lushene, Vagg & Jacobs, 1983; 20 items) Post-traumatic growth (PTGI, Tedeschi & Calhoun, 1996; 21 items; induction instruction: "since the lockdown"). The PTGI evaluates perceived positive changes such as shifting life priorities, closer relationships with others, developing new interests, etc. Trait anxiety (STAI-Trait questionnaire, Spielberger et al., 1983; 20 items) Sociodemographic variables (related to the Epidemiology WP) Depression (HADS questionnaire, Zigmond & Snaith, 1983; 14 items)
 
At 3, 6, 9, and 12 months (within the week following screening) State anxiety (STAI-State, 20 items) Depression (HADS, 14 items)

--	---

E) DESCRIPTION OF THE STUDY INTERVENTIONS

In this study, screening of patients and healthcare personnel will be performed using two or even three techniques depending on the result:

- **Repeated blood sampling, performed at inclusion (M0), Month 3 (M3), Month 6 (M6), Month 9 (M9), Month 12 (M12), plus on demand in the event of Covid-19 symptoms:**
 - a) Rapid serological test (TDR) — qualitative
 - Performed immediately on site.
 - Technique: immunochromatography strip detecting IgM / IgG.
 - b) Serology by ELISA — quantitative
 - Performed later on frozen samples.
 - c) Genotyping of FCGR2A and FCGR3A genes
 - Performed only at M0.
- **Nasopharyngeal swab (RT-PCR)**
 Detection of viral RNA.

This examination is performed with immediate result exclusively in the event of symptoms, irrespective of the rapid test result, for patients hospitalized in a Covid unit when such a unit exists within the center.

Results of RT-PCR tests performed in community settings (outside the hospital) will be collected via questionnaires.

- **Questionnaires** (Linked to the Work Packages — some are therefore optional)
 - Patients : Q1, Q2, Q3
 - Healthcare personnel : Q1, Q2, Q3, Q4, STAI (ETAT & TRAI), PTGI, HADS

TRIAL SCHEDULE

INCLUSION PERIOD:	12 months
DURATION OF PARTICIPATION PER SUBJECT:	12 months
MINIMUM PARTICIPATION TIME PER PATIENT:	12 months
OVERALL STUDY DURATION:	24 months
START OF THE CLINICAL TRIAL:	June 2020

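### WP 1 asks about neutralizing capacity after vaccination over the study, but its only criterion counts positive tests, so changes and group differences above the positivity cut go undescribed

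*Protocol*

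**What the plan says.** In the Protocol synopsis, section D, Secondary objective, WP 1 (mandatory for centers), one vaccination objective is to "Evaluate the neutralizing capacity of IgG (neutralization assays) after vaccination over the duration of the study". A separate objective in the same list is to count the subjects who have antibodies after vaccination.

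Under Completion evaluation criterion, WP 1, there are three vaccination criteria:

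- For binding IgG, a result and a level: "IgG-positive results on rapid TROD tests and semi-quantitative ELISA IgG titers in vaccinated individuals".
- For anti-Spike IgG, a count of the vaccinated subjects whose samples can be titrated.
- For neutralization, a count of positives: "Number of vaccinated individuals with positive neutralization test results".

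Only the last concerns neutralization. It names no titer or other level, no cut for positivity, no time point and no denominator.

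Two other places bear on the point. Section C, Expected outcomes, says the study will "study the evolution of immune response in cancer patients during treatment, compare it with long-term survivors and healthcare workers". Section E gives the sampling plan: "Repeated blood sampling, performed at inclusion (M0), Month 3 (M3), Month 6 (M6), Month 9 (M9), Month 12 (M12), plus on demand" if symptoms occur. The neutralization assay is not among the techniques listed there.

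**The concern.** Capacity is a graded quantity, and the objective asks how it behaves over the study. A count of positives records only which side of a cut each subject falls on. A subject whose neutralization drops several-fold but stays above the cut contributes the same before and after. Two populations that differ in level but are both mostly positive give nearly the same proportion.

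The protocol itself separates counting responders from evaluating capacity, since each has its own objective. It then measures capacity by counting responders. At stake is whether this objective can be answered, most of all if nearly all vaccinated subjects are positive and the comparison is between treated patients, patients in follow-up and personnel.

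**Working it through.** **1. The plan's own figure.** Section D, Number of subjects, gives 12,000 patients + 3,000 personnel = 15,000, which adds up. It is a recruitment estimate: "the number of subjects directly depends on the recruitment potential of each center". No alpha, power, effect or SD is stated, so there is no power figure to reproduce. Everything numerical below rests on assumptions.

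**2. Objective against criterion.**

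| | Objective | Criterion |
|---|---|---|
| Quantity | neutralizing capacity (a level) | positive or negative |
| Time | over the study | none named |
| Summary | not fixed | a number, no denominator |

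For binding IgG the same list keeps titers. For neutralization it does not.

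**3. What the count shows of waning.** Assume a normal log level whose mean lies k SD above the cut. The share positive is Φ(k). After a fall of 1 SD it is Φ(k − 1).

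- k = 3: 99.9% to 97.7%
- k = 2.5: 99.4% to 93.3%
- k = 2: 97.7% to 84.1%

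The same fall is nearly invisible from a high start and plain from a lower one.

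**4. Group differences: sample size.** Assume equal SD, two equal groups, two-sided 5%, 80% power and a difference d = 0.3 SD.

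On the level: n = 2(1.960 + 0.842)²/0.3² = 175 per group (rounded up).

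On positive or negative: with p₁ positive in the better group, p₂ = Φ(z(p₁) − 0.3), and the usual two-proportion formula gives n. The large-sample efficiency of the cut is φ(z)²/[p(1 − p)].

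| p₁ | p₂ | n per group | ratio to 175 | efficiency |
|---|---|---|---|---|
| 50% | 38.2% | 278 | 1.59 | 0.64 |
| 80% | 70.6% | 329 | 1.88 | 0.49 |
| 90% | 83.7% | 449 | 2.57 | 0.34 |
| 95% | 91.1% | 657 | 3.75 | 0.22 |
| 98% | 96.0% | 1,167 | 6.67 | 0.12 |

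This treats the level as known for everyone, including negatives.

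**5. Group differences: power when negatives carry no level.** Simulation with values below the cut tied; Mann-Whitney on levels against uncorrected chi-square on positive or negative.

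| n per group | shift | positive | power, level | power, count |
|---|---|---|---|---|
| 200 | 0.3 SD | 30% | 63% | 59% |
| 200 | 0.3 SD | 50% | 74% | 67% |
| 200 | 0.3 SD | 80% | 82% | 58% |
| 200 | 0.3 SD | 90% | 84% | 46% |
| 200 | 0.3 SD | 95% | 83% | 34% |
| 100 | 0.4 SD | 90% | 78% | 45% |
| 1,000 | 0.3 SD | 90% | 100% | 99% |
| 1,000 | 0.3 SD | 95% | 100% | 93% |

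At 3,000 per group both reach 100%. Repeat runs agree within simulation error.

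**The case against.** The strongest reply is that the protocol plans no test on this count. The main objective is descriptive, the size follows recruitment, and the comparison of immune response in section C is not tied to any neutralization test. This stands: a reader might infer that the trial loses a stated power, but there is none to lose. It does not rescue the criterion, because a description must still describe the quantity that the objective names.

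Second, the size of the loss depends on chosen settings. The cohort is large: "the cohort size has been estimated at 15,000 subjects distributed as follows", with 3,000 personnel. At 1,000 or more per group the count loses little except at very high positivity, and at 30% positivity the gain is only about 4 points. The protocol also raises immunosuppression in cancer patients, so low positivity cannot be excluded. This stands. The number of samples to be assayed and the sizes of the treatment subgroups are not given either.

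Third, a reader might infer that waning cannot be seen at all. That goes too far. If the test is repeated at the visits, falls across the cut show as a falling count, and binding IgG titers give indirect graded information. Only changes above the cut are hidden, and binding is not neutralization.

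Fourth, the protocol does not establish that the assay gives a graded reading. If it is purely qualitative, no information is being discarded by the criterion, and the remedy is to change the objective.

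Finally, a statistical analysis plan, not shown here, may add levels and time points. It may, but the protocol has already fixed this criterion as a count.

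**Conclusion.** The point holds as a mismatch between a graded, time-based objective and a criterion that only counts positives. It follows from the text and needs no assumption. Its consequence is limited: waning and group differences above the cut are not described.

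The numerical size is illustrative. It assumes a normal log level, equal SD, a two-sided 5% test and a graded assay. Under those assumptions the gain from using the level is large for subgroups of about 100 to 200 with high positivity (78% against 45%, and 84% against 46%, at 90% positive). It is about 4 points at 30% positivity with 200 per group. At 1,000 per group it is about 1 point at 90% positivity and 7 points at 95%.

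The documents do not support a claim that the study is underpowered, that all waning is invisible, or that positivity will saturate. This is a secondary criterion, and the primary criterion and the cohort size do not depend on it.

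**What to change.** Where the assay gives a graded reading, replace the criterion with: neutralization level (titer or percent inhibition, as read by the assay) in vaccinated individuals at each post-vaccination sample tested, by study population and treatment subgroup. Analyse it on the log or rank scale, with values below the limit treated as censored or tied. Report the number and proportion positive in addition, with the denominator.

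If the assay is only qualitative, restate the objective as the proportion positive at each visit, so that objective and criterion agree.

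The blood samples are already scheduled. The cost is a change of wording, export of the assay reading by the laboratory instead of the positive or negative call alone, and a little more analysis. The positive count is kept, so nothing is lost.

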--	---

	
c. Contact with infected individuals at work or at home d. Use of community care
 
Describe the incidence of Covid-19 infections among patients and healthcare personnel.
 
Compare the distribution of contamination risk factors among patients and those of the general population (Constances cohort).
 
Describe adherence to SARS-CoV-2 vaccination among personnel and patients.
 
WP 5 : PSYCHOLOGY OPTIONAL FOR CENTERS
 
Examine the evolution of state anxiety over time and determine whether perceptions of anxiety evolve, indicating a possible adaptation process.
 
Examine associations between post-traumatic growth, trait anxiety, sociodemographic variables, and the evolution of state anxiety over time.
 
Examine the evolution of depression over time and determine whether perceptions of depression evolve, indicating a possible adaptation process.
 
Examine associations between post-traumatic growth, trait anxiety, sociodemographic variables, and the evolution of depression over time.

INCLUSION CRITERIA:	
 1) Age \geq 18 years; 2) Population from a CLCC meeting one of the following three definitions: 
  patients undergoing treatment,  patients in follow-up (having completed their treatment more than one year prior to inclusion),  healthcare personnel; 3) Subjects having had or not had an infection compatible with, or confirmed as, Covid-19; 4) Subjects informed and having signed the informed consent form; 5) Subject affiliated with a social security system.
NON-INCLUSION CRITERIA:	
 1) Refusal to provide consent; 2) Patients unable to give consent or presenting psychiatric history; 3) Inability to comply with medical follow-up for geographical, social, or psychological reasons; 4) Individuals under legal protection (guardianship or curatorship); 5) Individuals deprived of liberty by judicial or administrative decision.
PRIMARY EVALUATION CRITERION:	
Biological data: Serological status (rapid immunochromatographic test) and IgM and IgG titers (enzyme immunoassay, ELISA type), performed at M0, M3, M6, M9, and M12. Collection via questionnaire of results from tests detecting SARS-CoV-2 viral genome (RT-PCR molecular test) performed in community settings
 
Clinical data: Follow-up questionnaire on clinical signs suggestive of Covid-19.

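### The WP2 fatal proportion counts infections already survived at inclusion in its denominator, so it understates the fatality of infections arising after inclusion

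*Protocol*

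**What the plan says.** All references are to the protocol synopsis, part D unless stated.

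- **Severity criterion** (Completion evaluation criterion, WP 2): "Number of Covid-19-related deaths, severe infections (requiring oxygen therapy), prolonged symptomatic infections, moderate infections, and asymptomatic infections, relative to all subjects in the population" and, continuing, "with seropositivity and/or a positive RT-PCR test, as well as duration of the symptomatic phase". No date of infection restricts this set.
- **Risk factors** (same section): "Among subjects in the population with seropositivity and/or a positive RT-PCR test, factors significantly associated with severe forms / mortality among the following". This is the same set of positives.
- **Eligibility** (Inclusion criteria 3 and 4): "Subjects having had or not had an infection compatible with, or confirmed as, Covid-19" and "Subjects informed and having signed the informed consent form".
- **Timing**: the Population entry places subjects in their categories "between March 2020 and the end of the pandemic". The Trial schedule gives a June 2020 start, 12 months of inclusion, 12 months of participation per subject, and last follow-up in May 2022.
- **Testing**: serology starts at M0 and is repeated at M3, M6, M9 and M12 (Primary evaluation criterion). Results of community RT-PCR tests come from questionnaires.
- **Reinfection** is foreseen (WP 2): "Reinfection cases are defined as recurrence of clinical symptoms and/or positive viral PCR and/or positive IgM serology after a symptom-free interval".
- **Role of severity**: the main objective is a database to "describe Covid-19 infections (incidence and severity) among CLCC patients and personnel", and the WP 2 objective lists fatal as one of the severity classes to be described by group.

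**The concern.** Numerator and denominator cover different periods. A subject whose infection resolved before inclusion counts as a positive, through antibodies at M0 or an earlier RT-PCR result. The matching death from an infection in that period cannot be counted, because that person could not consent. Such subjects can add a Covid-19 death only if they are still ill at inclusion or are later reinfected.

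The reported death proportion therefore depends on how late subjects were enrolled as well as on how lethal the infection is. WP2 is mandatory for all centres, and a reader will naturally take deaths over infected subjects as a fatality. If the share of survived infections differs between groups, comparisons of fatality between them are also distorted.

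**Working it through.** The protocol states no fatality figure for WP2, so there is nothing to reproduce. The check is a mixture identity.

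**Inputs.** The denominator, eligibility and dates come from the protocol as cited. The following are not in the protocol and are assumed:
- d: fatality of infections arising after inclusion.
- f: share of positives whose infection was already survived at inclusion.
- q: later Covid-19 death risk of those subjects divided by d. If reinfections are as fatal as first infections, this is the fraction reinfected.

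**Step 1: dilution.** Reported proportion = (1 − f)d + f·q·d, so reported/d = 1 − f(1 − q). The ratio does not depend on d and is below 1 whenever f > 0 and q < 1.

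| | f = 20% | f = 40% | f = 60% |
|---|---|---|---|
| q = 0 | 0.80 | 0.60 | 0.40 |
| q = 0.10 | 0.82 | 0.64 | 0.46 |
| q = 0.20 | 0.84 | 0.68 | 0.52 |

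Example: 1000 positives, d = 10%, f = 40%, q = 0. There are 600 × 0.10 = 60 deaths. The stated rule reports 60/1000 = 6.0%; among infections arising after inclusion it is 60/600 = 10.0%.

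**Step 2: scale of f from the dates (illustration only).** The time from March 2020 to inclusion is t = 3 months for the first subject and 15 for the last; follow-up is 12 months. With r the ratio of the infection rate before inclusion to that after, f = r·t/(r·t + 12). At r = 1: 3/15 = 20%, 15/27 = 56%, and at the mean t = 9 under even recruitment 9/21 = 43%. At r = 0.5: 4.5/16.5 = 27%. At r = 2: 18/30 = 60%.

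**Step 3: other classes.** Let s be the severe non-fatal risk.
- Severe non-fatal, reported/true = (1 − f) + f/(1 − d). For f = 20%, 40%, 60% this is 1.02, 1.04, 1.07 at d = 10%, and at most 1.01 at d = 1%.
- Severe and fatal pooled, reported/true: 0.95, 0.90, 0.84 (d = 10%, s = 20%), or 0.97, 0.94, 0.91 (d = 1%, s = 5%).

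**Step 4: group comparisons.** At q = 0 the fatality ratio of group a to group b is multiplied by (1 − fa)/(1 − fb). This is 1.00 if the shares are equal, 0.80/0.60 = 1.33 for 20% against 40%, and 0.75 the other way round.

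**Step 5: cost of restricting to infections after inclusion** (d = 10%, q = 0; f = 20%, 40%, 60%).
- Standard error of the death proportion: 1.24, 1.63, 2.42 times larger. In the example, √(0.10 × 0.90/600) = 0.0122 against √(0.06 × 0.94/1000) = 0.0075. Relative to the estimate it is 0.99, 0.98, 0.97 times.
- Log odds ratio for death alone (balanced binary factor, no effect): standard error up 1%, 2%, 3%.
- Severe and fatal pooled (s = 20%): events per 1000 positives fall from 284 to 240, 269 to 180, and 253 to 120. For the same balanced factor, the standard error of the log odds ratio rises by √(203.5/168) = 1.10, √(196.6/126) = 1.25 and √(189.2/84) = 1.50, where each term is N × p(1 − p).

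**The case against.** *The target is the reviewer's.* WP2 describes severity among positive cohort members, and no passage names the fatality of infections arising after inclusion as the quantity sought. This stands in part: the proportion is correct as arithmetic on the stated set. But fatal is a named class and severity is in the main objective. A death proportion whose denominator holds people who could not have been counted as deaths from that infection has no clear clinical reading.

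*The SAP may split the positives.* It may. The point is not that detail is missing: the protocol itself fixes the denominator, without a split.

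*Subjects positive at M0 can still die of Covid-19.* True, and q allows for it. The dilution shrinks but keeps its direction while q < 1.

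*The size is unsupported.* This stands. A reader might take the date-based 43% as an estimate of f. The documents do not support that. It assumes a constant infection rate and that old infections are found as readily as new ones. The protocol treats IgG persistence to M12 as an open question (WP 1) and calls antibody kinetics poorly characterised in mild cases and in patients with cancer (Rationale). Later infections, by contrast, are sought every three months and when symptoms occur. Poorer detection of old infections acts like r below 1, so the value leans high. The March 2020 date also defines when people belong to the study categories; it is not a stated look-back period for infection.

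*Restricting every risk-factor analysis would cost too much.* This also stands. For severe and fatal forms pooled, the loss of precision is 10% to 50% under the assumptions above, against a bias in ratios that arises only if f differs between groups.

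**Conclusion.** The concern holds for the fatal proportion and for any analysis of death alone. The stated WP2 denominator understates the fatality of infections arising after inclusion by the factor 1 − f(1 − q). The direction follows from the protocol's own rules. The size is unknown, because neither f nor q is given: 0.80, 0.60 and 0.40 are values for assumed f of 20%, 40% and 60% with q = 0. The formula also assumes equal fatality before and after inclusion and correct classification of infections by date.

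Three stronger readings are not supported:
- That all severity classes are distorted. Non-fatal past infections can be recorded at inclusion, and the severe non-fatal class is off by a factor of only 1.00 to 1.07.
- That the risk-factor ratios are biased. They are distorted only if f differs between the groups compared, and the protocol gives no information on that.
- That the protocol promises a fatality rate for all infections since March 2020. It does not.

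Separately, seropositivity is not limited to antibodies from infection, although vaccinated subjects are followed. Positives through vaccination alone would enlarge the denominator further; they are outside the figures above.

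**What to change.** 1. Report the death proportion, and any analysis of death alone, among infections first detected after inclusion: no evidence of infection at M0 by serology, RT-PCR or questionnaire, then a positive RT-PCR or a seroconversion not attributable to vaccination.
2. Show subjects positive at M0 separately, labelled as infections survived to inclusion, and count there any later Covid-19 deaths among them.
3. Keep all positives for the non-fatal severity classes and for risk factors of severe and fatal forms pooled. Adjust for or stratify by M0 status, and give the set of infections after inclusion as a sensitivity analysis.

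This needs no new visit or sample, only a split on data already collected and one rule for seroconversion after vaccination. The price is a smaller set and a wider absolute confidence interval for the death proportion; precision relative to the estimate is almost unchanged. The split is not perfect: some earlier infections undetected at M0 will still be classed as new.
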